7.3 Patient Discontinuation, Site Termination or Study Termination

7.3.1 Withdrawal of Individual Patients Prior to Study Completion

Considering the retrospective study design, no withdrawal of individual patients prior to study end is expected.

7.3.2 Study or Study Site Termination

The Sponsor reserves the right, at any time, to discontinue selection of additional patients into the study, at any site; or to discontinue the study for administrative reasons.

8 STUDY POPULATION

8.1 Sites

Site selection will aim to recruit sites where investigators are certified XEN 45 Gel Stent surgeons and are known to have implanted XEN 45 Gel Stent in the time period being studied. A sample of ophthalmologists working in experienced glaucoma centers will thereby be selected.

8.2 Patients

The study population will include patients with one or both eyes with open angle glaucoma that underwent XEN 45 Gel Stent implantation.

8.2.1 Inclusion Criteria

A patient's eye must meet **all** of the following criteria to be eligible for participation in the study.

1. Eye treated with XEN 45 Gel Stent for open angle glaucoma as a standalone procedure or in combination with phacoemulsification
2. XEN 45 Gel Stent was implanted between 1 January 2014 and 1 October 2015

8.2.2 Exclusion Criteria

None

8.2.3 Minimum Required Dataset

Medical charts that do not include the following data will not be selected for the study. Therefore, if no data is available within the charts at the study site, before selecting the chart for inclusion in the study it must be established that certain key data from other locations will be made available for investigators for data entry.

Patient characteristics

- Age
- Gender

Intraocular Pressure

- IOP at baseline (i.e. medicated IOP) and until last visit (1 October 2018 or until the date on which the patient received a SSI for glaucoma, whichever occurs first)
- Number of topical IOP-lowering medication prescribed for the study eye at baseline and until last visit (1 October 2018 or until the date on which the patient received a SSI for glaucoma, whichever occurs first)

Secondary surgical intervention

- Date of the SSI for glaucoma, if any

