7 STUDY CONDUCT

7.1 Overall Design of the Study

This is a retrospective, non-interventional, observational, multi-center, chart review study to be conducted in patients who underwent placement of the XEN 45 Gel Stent as a standalone procedure or in combination with phacoemulsification from 1 January 2014 to 1 October 2015. For patients implanted bilaterally, both eyes can be entered into the study database if they both meet eligibility criteria. Data from approximately 150 eyes will be collected by retrospective review of medical charts in 5 European countries. Countries considered at time of protocol development are: Austria, Belgium, Germany, Spain and the United Kingdom. Sites will be centers with certified XEN 45 Gel Stent surgeons known to have implanted XEN 45 Gel Stent in the time period being studied.

Patients' medical charts will be extracted until the target number of eyes for the primary analysis has been reached. Site personnel will be required to complete a screening log for patients treated with XEN 45 Gel Stent on or after 1 January 2014 to identify eligible patients (see Section 9.2). For each eye selected, all retrospective data available from baseline (i.e. day when decision was made to implant XEN 45 Gel Stent) until Last Visit (i.e. date of the last follow-up visit available prior to 1 October 2018 or date on which the patient had a SSI for glaucoma, whichever occurs first) will be extracted from existing medical records. The study will not impose any separate patient visits to the site. In case key data are not available within the charts at the site, site personnel will be asked to liaise with the patients' treating ophthalmologist to request data to be made available for investigators for data entry.

A feasibility assessment will be conducted prior to the study conduct in the considered countries to assess whether targeted sites have access to complete patient records including patient's follow up after implantation of XEN 45 Gel Stent, to assess the number of eligible eyes, and to assess sites willingness to participate in the study.

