14 STATISTICAL METHODS

14.1 Sample Size

To answer study primary objective, this chart review study plans to accrue a minimum of 60 study eyes that have had at least 3 years of follow-up data without a SSI for glaucoma after the initial implant with XEN 45 Gel Stent.

Data from the Allergan study MS-001 demonstrated that the mean IOP reduction from baseline differed slightly among the 7 visits (see below) in the 24-month post-implant period. The absence of a clear waning-out trend suggests that the effect of XEN 45 Gel Stent implantation on IOP reduction may last to Month 36 and beyond. The minimum mean reduction (negative sign stands for reduction) in IOP among the visits was -5.6 (± 6.32) mmHg, which was observed at Month 3. This value was then taken as an initial estimate for the mean reduction projected for Month 36. The 95% confidence interval (CI) of the projected mean reduction afforded by a sample of 60 study eyes is -7.2 to -4.0 mmHg. That is, the half-length of the interval is 1.6 mmHg, which provides a reasonable precision for the estimate of the projected mean reduction in IOP.

Table 4 Result from the MS-001 Study

Visit	Number of study eyes	Mean (SD) change in IOP from medicated baseline (mmHg)
Month 1	167	-6.3 (6.41)
Month 3	167	-5.6 (6.32)
Month 6	168	-6.4 (4.92)
Month 9	134	-6.1 (5.68)
Month 12	161	-6.7 (5.41)
Month 18	149	-7.1 (5.10)
Month 24	149	-6.2 (4.94)

The MS-001 study enrolled 199 patients (218 study eyes). In this study, patients' discontinuation rate tended to be linear over the 2-year follow-up period, with an overall study discontinuation rate of approximately 20%. Using data from the MS-001 study, it could be assumed that 30% of the eyes selected for this study have less than 3 years of follow-up data. Taking into consideration that MS-001 study was a clinical trial and that patient retention rate is expected to be lower in a real-world setting, the study will aim to select 150 eyes to ensure obtaining a minimum of 60 eyes with at least 3 years of follow-up data.

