1.6. Study Design

This is a retrospective, non-interventional, observational, multi-centre, chart review study conducted in patients who underwent placement of the XEN 45 Gel Stent as a standalone procedure or in combination with phacoemulsification from 1 January 2014 to 1 October 2015.

For each eligible eye, all retrospective data available from baseline (i.e. day when decision was made to implant XEN 45 Gel Stent) until Last Visit (i.e. date of the last follow-up visit available prior to 1 October 2018 or date on which the patient had a SSI for glaucoma, whichever occurs first) are extracted from existing medical records into the electronic CRF (eCRF) in Dacima.

If both eyes from the same patient meet eligibility criteria, each eye is included in the study database with a unique identifier and eyes are paired in the electronic data capture system (EDC). See section 4 for how bilateral eyes included in the study are handled in the analyses.

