1.7. Study Population

The study population includes patients with one or both eyes with open angle glaucoma that underwent XEN 45 Gel Stent implantation.

Patients meeting the following criteria are eligible for participation in the study:

1. Eye treated with XEN 45 Gel Stent for open angle glaucoma as a standalone procedure or in combination with phacoemulsification
2. XEN 45 Gel Stent was implanted between 1 January 2014 and 1 October 2015
3. Charts contain minimum required data (age, gender, IOP at baseline until last visit, number of topical IOP-lowering medications prescribed for the study eye from baseline until last visit, date of the SSI for glaucoma if applicable)

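### Protocol 8.2.3 ends the required data at a calendar date, against the plan's own Last Visit definition; applied literally, it drops SSI-free eyes lost to follow-up but keeps early SSI eyes

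*Protocol*

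**What the plan says.** Protocol 8.2.3 works as a gate: "Medical charts that do not include the following data will not be selected for the study". The list that follows includes "IOP at baseline (i.e. medicated IOP) and until last visit (1 October 2018 or until the date on which the patient received a SSI" (the earlier of the two), and "Number of topical IOP-lowering medication prescribed for the study eye at baseline and until last visit (1 October 2018", with the same SSI alternative. Here the last visit is explained as a calendar date or an SSI date.

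Protocol 7.1 defines Last Visit as the "date of the last follow-up visit available prior to 1 October 2018", or the SSI date if that is earlier. The synopsis (duration of study) and Table 3 footnote a agree. So does SAP 1.6: "Last Visit (i.e. date of the last follow-up visit available prior to 1 October 2018 or date on which the patient had a SSI", taking the earlier of the two.

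SAP 1.7 makes the minimum dataset its third eligibility criterion: "Charts contain minimum required data (age, gender, IOP at baseline until last visit, number of topical IOP-lowering medications prescribed" and so on. It refers to the last visit but gives no date.

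Protocol 14.1, on the size of the study, says that "it could be assumed that 30% of the eyes selected for this study have less than 3 years of follow-up data". Protocol 8.2.2 lists no exclusion criteria.

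**The concern.** Under the 8.2.3 wording, an SSI-free eye needs data up to 1 October 2018, while an eye with an SSI needs data only up to the SSI. Whether a short chart is selected would then depend on its outcome. The planned Kaplan-Meier analysis of time to SSI (Protocol 14.2.5.2, SAP 4.4.1 and 4.6) needs SSI-free eyes that leave early to be present and censored. If they are never selected, the curve comes from a set enriched for SSI. Eyes with a sound 3-year measurement but no later visits would also be refused, although they carry the primary outcome.

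**Working it through.** **1. The plan's own figure.** Inputs from Protocol 14.1: mean change -5.6 mmHg, SD 6.32, n = 60. Half-width = 1.96 × 6.32/√60 = 1.60, so the interval is -7.2 to -4.0 mmHg, as stated. The point at issue does not alter this figure: it concerns which eyes are selected, not the precision from 60 of them.

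**2. The same chart under the two wordings.**

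| Chart | 8.2.3 read literally | Last Visit as in 7.1 and SAP 1.6 |
|---|---|---|
| Ends in 2016, no SSI | refused | selectable |
| Ends in 2016 with an SSI | selectable | selectable |

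**3. Check against 14.1.** Discontinuation in MS-001 was about 20% over 2 years and roughly linear, so 10% per year, or 30% at 3 years. That gives 150 × 0.70 = 105 eyes with 3 years. The target of 60 from 150 is 40%, so the plan tolerates a 60% shortfall; for 30% alone, 60/0.70 = 85.7, or 86 eyes, would do. The latest implantation date, 1 October 2015, is exactly 36 months before the cut-off. Under the literal 8.2.3, every selected SSI-free eye therefore has at least 3 years, and only SSI eyes could fall short. A 30% shortfall derived from discontinuation could not arise. The two sections cannot both operate.

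**4. Eyes refused if 8.2.3 is applied literally.** Assumption: loss continues at 10% per year, and SSI is ignored. Loss by cut-off = 0.10 × months/12. Share of 3-year eyes still refused = (loss − 0.30)/0.70.

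| Implantation | Months to cut-off | Lost by cut-off | 3-year eyes still refused |
|---|---|---|---|
| 1 January 2014 | 57 | 47.5% | 25% |
| 31 December 2014 | 45 | 37.5% | 10.7% |
| 1 October 2015 | 36 | 30% | 0% |

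Under the Last Visit definition none is refused for loss to follow-up.

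**5. Effect on SSI.** The documents give no SSI rate, so this is an illustration. Assume constant and independent hazards of SSI (λ) and loss (μ), with T years to cut-off. Among all eyes, the share with SSI before loss is a = λ/(λ+μ) × (1 − exp(−(λ+μ)T)), and the share free of both at cut-off is b = exp(−(λ+μ)T). The literal rule keeps only these two groups, so the SSI share among selected eyes is a/(a+b).

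With T = 3, true SSI 10% and loss 30%: λ/(λ+μ) = 0.228 and b = 0.90 × 0.70 = 0.63, so a = 0.228 × 0.37 = 0.0844 and a/(a+b) = 0.0844/0.7144 = 11.8%.

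| True 3-year SSI | Shown at 30% loss | Shown at 60% loss |
|---|---|---|
| 10% | 11.8% | 15.5% |
| 20% | 23.2% | 29.4% |
| 30% | 34.2% | 41.9% |

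With T = 3, no selected eye is censored before 3 years, so the Kaplan-Meier estimate at 3 years equals this share. If lost eyes were kept and censored, Kaplan-Meier would recover the true value under the same independence assumption. For an eye implanted on 1 January 2014 (T = 4.75), the first row becomes a true 15.4% shown as 19.7% or 29.4%.

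**The case against.** The strongest reply is that the plan does not intend this. SAP criterion 3 has no calendar date, and SAP 1.6 defines Last Visit as the latest visit on record, so under the SAP an SSI-free chart ending in 2016 qualifies. Protocol 14.1 sets 150 eyes precisely because some selected eyes will be lost. Taken strictly, 8.2.3 asks for data up to one calendar day in a study that schedules no visits, so the date is more naturally an administrative cut-off. Table 2 footnote b and SAP 1.8 use similar shorthand for the extraction window. All of this stands as evidence of intent. It does not remove the risk: 8.2.3 is the selection rule in the protocol that sites receive in their study kit, and it states its own end point.

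The second reply is that misuse would show. The screening log records Last Visit and the reason for non-selection, and Protocol 14.3.2 plans to compare selected and non-selected eyes. This stands in part. The log has no separate SSI field, and its Last Visit date merges SSI with last follow-up, so the comparison would struggle to show selection by SSI. Nor would it bring refused eyes back.

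The third reply concerns size. A reader might take the true SSI rate s and a loss fraction l and quote s/(1 − l), for example 0.10/0.70 = 14.3%. That is a crude share: it counts every SSI as occurring before loss, and it is not the planned Kaplan-Meier estimate. The time-to-event calculation gives 11.8% for the same inputs. The objection stands on this.

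**Conclusion.** The contradiction over the last visit is established from the text. The bias is conditional on sites applying 8.2.3 literally. In that case SSI frequency and the SSI curve are biased towards more SSI: by about 2 to 12 percentage points at 3 years over the assumed range (true SSI 10% to 30%, loss 30% to 60%, constant independent hazards). Up to about a quarter of the earliest-implanted eyes with 3-year data would also be refused, if loss runs at 10% per year.

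Three stronger conclusions that a reader might draw are not supported. The SAP does not itself make data up to 1 October 2018 an eligibility criterion. The documents do not show a design meant to keep only complete charts or failures; 14.1 points the other way. And the direction of any bias in IOP change cannot be derived from them. The Year 3 and Year 4 IOP analyses are in any case already limited to eyes with enough follow-up (Protocol 14.2.4 and 14.2.5.1), so an IOP result that describes well-followed eyes is largely the stated design. No figure is offered for success or AESI rates.

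**What to change.** - Protocol 8.2.3: replace the two dated parentheses, for IOP and for medication count, with the Last Visit definition of Section 7.1.
- SAP 1.7, criterion 3: keep the list of required data and add a cross-reference to the Last Visit definition in SAP 1.6. The parenthesis there is the data list itself and must not be overwritten.
- Both documents: state that follow-up ending before 1 October 2018 without an SSI is not a reason for non-selection, and that such eyes are censored at their last visit in the time-to-SSI analysis.

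No new requirement for a post-implantation IOP value is needed. It could remove eyes whose SSI came before any recorded IOP, and the synopsis already asks for documented post-operative follow-up.

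The cost is a few lines in each document and some additional short charts to extract.

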6.2 Key Variable Definitions

Qualified success of implantation of the XEN 45 Gel Stent will be defined as $\geq 20\%$ reduction from medicated baseline with no SSI for glaucoma and no clinical hypotony while staying on the same number or fewer topical IOP-lowering medications than at baseline.

Complete success of implantation of the XEN 45 Gel Stent will be defined as $\geq 20\%$ reduction from medicated baseline with no SSI for glaucoma and no clinical hypotony while taking no topical IOP-lowering medications.

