14.2.1 Study Populations and Analysis Methods

- Analysis Population: all eyes selected and meeting the selection criteria.
- Subgroups analyses will be conducted in eyes that did or did not undergo phacoemulsification. Additional subgroups may be further considered in the SAP.

Continuous variables will be described by their mean, standard deviation, median, upper and lower quartiles, extreme values (minimum and maximum) and the number of missing data.

Categorical variables will be described by the number and percentage of each response and the number of missing data.

Figures will be generated, when appropriate, to describe change in parameters over time.

Some of the data will only be collected if they occurred within study-defined time windows (see Section 7.2). Since all data within the defined time windows will be collected, more than one value could be available per time window for a given parameter. Rules to determine which value will be used for the analysis will be defined in the SAP.

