3.4. Missing Data

The eCRF is designed to ensure that no questions are left unanswered. If 'unknown' is selected, this will be included as such in the results and tabulated for all variables. Central tendencies will not be measured for continuous unknown data, only counts and percentages will be recorded.

In some cases, imputation of unknown variables may be conducted if the variable is to be used in calculations for another variable or analysis. For example, the eCRF allows some dates to be incomplete (i.e. day is unknown) if it is not available in the medical chart. This may impact accurate calculation of durations, resulting in an imputation needing to be made. If the day is missing, the date will be imputed as the 15th of the month, except in cases where this would lead to a negative duration, in which case the 1st or last day of the month will be used (whichever addresses the negative duration). No imputation will be made for missing month/year; these are classified as date unknown within the eCRF. All imputed values will be documented and presented as footnotes in the result tables.

4. Planned Analyses

The analyses detailed below will be performed to meet the project objectives. There will be two analysis populations specified for the analyses to be conducted:

- The **Effectiveness Population** consists of all eligible study eyes in the population except in instances when a patient has contributed both eligible eyes in the study, then only the eye that received the Xen-45 implant first will be selected; this eye will be presented in tables as the 'primary eye'. All results tables in the Effectiveness Population will include stratified results presenting data for the primary eye, as well as data on all included patient eyes (even if both eyes from a single patient are included).
- The **Safety Population** consists of all eligible study eyes in the population.

All results tables will be stratified by Xen-45 implant only, implant plus phacoemulsification, and total population. Sensitivity analyses will be conducted to assess study results in the 'second eye' (i.e. not the primary eye as described above), for patients where both eyes were included. The sensitivity analyses will focus on the tables conducted using the Effectiveness Population.

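### Making the SSI date a condition of selection can refuse only eyes that had an SSI, so any undatable SSI would lower the SSI rate and raise qualified/complete success, by an unknown amount

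*Protocol*

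**What the plan says.** Protocol 8.2.3 defines a minimum dataset and states that "Medical charts that do not include the following data will not be selected for the study". Its last item is "Date of the SSI for glaucoma, if any". SAP 1.7 turns the same list into eligibility criterion 3, worded there as "date of the SSI for glaucoma if applicable".

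Two provisions soften the rule:

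- **Retrieval.** Where the site's chart has gaps, Protocol 8.2.3 says that before selection "it must be established that certain key data from other locations will be made available for investigators for data entry". Protocol 7.1 and 14.3.3 add that sites will approach the treating ophthalmologist, and that feasibility work checks access to complete records.
- **Partial dates.** SAP 3.4 says "the eCRF allows some dates to be incomplete (i.e. day is unknown) if it is not available in the medical chart", and sets a missing day to the 15th unless that gives a negative duration. For larger gaps: "No imputation will be made for missing month/year; these are classified as date unknown within the eCRF". It does not say whether the SSI date is among the dates covered.

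SSI is also an outcome. Qualified success in Protocol 6.2 requires a 20% "reduction from medicated baseline with no SSI for glaucoma and no clinical hypotony while staying on the same number or fewer" topical medications, and complete success carries the same no-SSI condition. Time to SSI is analysed by Kaplan-Meier (Protocol 14.2.5.2; SAP 4.4.1 and 4.6). The protocol analyses success in its "Analysis Population: all eyes selected and meeting the selection criteria". The SAP's Effectiveness and Safety Populations are likewise drawn from eligible eyes.

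**The concern.** An eye that never had an SSI meets this item automatically. Only an eye that had one can fail it, for example when the chart shows that glaucoma surgery was done elsewhere but not when. Selection then depends on a post-implant outcome, although Protocol 8.2.2 lists no exclusion criteria and 14.3.2 intends eyes to be taken in chronological order whatever their other features.

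At stake are a secondary objective (success) and the SSI analysis. A refused eye is a known failure that leaves both numerator and denominator, and the resulting error favours the device. It would also be hard to see afterwards. The eye is not in the database, and the data are anonymised with no queries issued (Protocol 12 and 14.3.3).

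**Working it through.** **The plan's own figure.** The documents give no figure for SSI or for undated SSIs. The one precision statement, in Protocol 14.1, concerns IOP change: 1.96 × 6.32/√60 = 1.60, so −5.6 ± 1.6 gives −7.2 to −4.0 mmHg. It reproduces and does not bear on this point.

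**Inputs.** The 150 eyes come from Protocol 14.1 and are used here as the number otherwise eligible. Three inputs are assumptions:

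- *s*, the true proportion of eyes with an SSI
- *f*, the share of those whose date stays unobtainable after retrieval
- *q* = 50%, the true success proportion with SSI eyes counted as failures

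**Formulas.** Eyes refused = 150·s·f. Observed SSI proportion = s(1−f)/(1−sf). Observed success = q/(1−sf), because refused eyes are all failures and only the denominator shrinks.

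| s | f | Eyes refused | Observed SSI | Observed success (true 50%) |
|---|---|---|---|---|
| any | 0 | 0 | unchanged | 50.0% |
| 10% | 10% | 1.5 | 13.5/148.5 = 9.1% | 75/148.5 = 50.5% |
| 10% | 20% | 3 | 12/147 = 8.2% | 75/147 = 51.0% |
| 20% | 10% | 3 | 27/147 = 18.4% | 75/147 = 51.0% |
| 20% | 20% | 6 | 24/144 = 16.7% | 75/144 = 52.1% |
| 30% | 50% (extreme) | 22.5 | 22.5/127.5 = 17.6% | 75/127.5 = 58.8% |

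Across s and f of 10-20%, the SSI proportion falls by 0.9 to 3.3 points and success rises by 0.5 to 2.1 points.

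**Direction for the Kaplan-Meier curve.** Without censoring, let *d* of *n* eyes have had an SSI by time *t*. Refusing an eye whose SSI came by *t* gives (d−1)/(n−1), which is below d/n whenever d < n. Before that eye's own SSI time the estimate is d/(n−1), very slightly above d/n. The downward direction therefore holds from the refused eye's SSI time onward, and so at the end of follow-up.

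**Which summaries are affected.**

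- *SSI proportion and Kaplan-Meier analyses:* yes.
- *Qualified/complete success:* yes, if eyes with an earlier SSI stay in the denominator as failures. Protocol 6.2 read with 14.2.1 implies this. SAP 4.4.1 does not state the denominator. If it were limited to eyes with data in the window, eyes with an earlier SSI would already be absent.
- *20%-reduction and IOP-threshold proportions:* not through removal of failures, because Protocol 14.2.5.2 and SAP 4.4.1 already exclude SSI eyes.
- *Primary 3-year IOP and medication change:* little. Extraction stops at the SSI, so an eye with an SSI before the Year 3 window does not contribute anyway. Only an undated SSI after that window would remove a usable value.

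**Would the planned check show it?** Protocol 14.3.2 compares selected with non-selected eyes and describes reasons for non-selection. The log (Protocol 10.1, Table 3) holds eye side, indication, implant date, Last Visit and the reason. Last Visit is the earlier of last follow-up and SSI date, so it does not identify an SSI. The example reasons are generic, such as incomplete access to records.

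**The case against.** The strongest reply is that few eyes, perhaps none, are affected. Missing key data are sought elsewhere before a chart is refused, feasibility work checks for complete records, and a missing day may be imputed. Nothing in the documents shows that even one eye is lost. This stands: the effect is a risk of unknown size. It does not remove the point, because the plan still refuses an SSI that stays undated, and Protocol 14.3.3 accepts that some records will not cover every encounter.

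The assumed effects are also small against sampling error. With 150 eyes, the 95% half-width at a 10% rate is 1.96 × √(0.10 × 0.90/150) = 4.8 points. That stands too, but a one-directional error is not reflected in a confidence interval.

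The date has a real purpose: it ends extraction, separates IOP before and after the SSI, and gives the event time. That is a reason to collect it, not to refuse the eye without it.

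A reader might infer more than the documents support:

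- *That eligibility as a whole removes failures.* The IOP and medication items in 8.2.3 run to 1 October 2018 or to the SSI, whichever is first. Read literally, eyes without an SSI face the longer requirement, which could offset this item. The net direction of the whole minimum dataset is not shown.
- *That the eCRF already makes refusal needless.* The unknown-date class in SAP 3.4 would show this only if it applies to the SSI date, which is not stated.

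**Conclusion.** The point holds for this one item. As written, an eye with a known SSI that cannot be dated after retrieval is refused. Through this item alone, the SSI proportion and the Kaplan-Meier cumulative estimate by the end of follow-up can only move down, and qualified/complete success can only move up where SSI eyes count as failures in the denominator.

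The size rests entirely on assumed values of *s* and *f*. It is zero if every SSI can be dated, and about 0.9 to 3.3 points on SSI and 0.5 to 2.1 points on a 50% success rate over the moderate range. It does not undermine the primary result. It is worth correcting because the error favours the device, the planned check would not reveal it, and the correction is small.

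**What to change.** 1. In Protocol 8.2.3 and SAP 1.7, replace the item with: *SSI for glaucoma: yes or no; date if known.*
2. Add SSI yes/no to the screening log (Protocol Table 3), and report it for selected and non-selected eyes in the comparison planned in Protocol 14.3.2.
3. For an SSI without month and year, record two dates: the last visit known to be free of SSI, and the first record that reports the SSI, no later than 1 October 2018. Use IOP data only up to the first date.
4. Treat the event as interval-censored between the two dates. Alternatively, place it at the midpoint and repeat the Kaplan-Meier analysis at each bound as a sensitivity analysis.
5. State in SAP 4.4.1 that such an eye stays in the qualified/complete success denominator as a failure in every window after the upper bound. Analyse windows between the bounds both ways, as failed and as not yet failed, as a sensitivity analysis.

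The cost is one changed line in each document, one log field, two date fields for a few eyes, and a short analysis rule. The downside is approximate event times for those eyes and slightly less favourable SSI and success figures. If selection is already under way, charts refused on this ground would need to be screened again.
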